#### 9.4.5 [REDACTED] and Exploratory Analysis

### 9.5 Interim Analyses

There are no formal interim futility and interim efficacy analyses in this study.

### 9.6 Safety Review Committee

This study will have an SRC. The SRC will conduct scheduled reviews of safety and other relevant data. In addition, The SRC will meet to review any of the following events should they occur during the study:

- Any death due to acalabrutinib (per Investigator)
- Any Grade 4 hemorrhage due to acalabrutinib (per Investigator)

The SRC will consist of the AstraZeneca Study Physician or delegate, Principal Investigator or equivalent delegate from active investigational sites, and Global Safety Physician or delegate. Other attendees may also be invited as appropriate.

Details on the process of ongoing evaluation of safety data by the SRC and the committee composition is described further in the SRC charter.

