## Disclosure Statement

This is a single-arm, treatment study that is not blinded.

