## Safety Review Committee

An SRC will be established to conduct scheduled reviews of safety and other relevant data, enable early identification of safety signals in the study, and minimize the risk to participants during the study, in accordance with the SRC charter (see Section 9.6 for details).

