#### 2.3.1.1 Hemorrhage

Bleeding events, some fatal, including central nervous system, respiratory, and gastrointestinal hemorrhage, have been reported in participants treated with acalabrutinib.

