#### **Medications Prohibited Through Day 14**

**Strong CYP3A inhibitors or inducers:** Drug-drug interactions may occur with some of the drugs being used as BSC (eg, drugs that are strong inducers or strong inhibitors of CYP3A). Concomitant administration with a strong inhibitor of CYP3A has the potential to increase

acalabrutinib exposure. Conversely, concomitant administration with a strong inducer of CYP3A has the potential to decrease exposure of acalabrutinib and could reduce efficacy. Therefore, the concomitant use of strong inhibitors or inducers of CYP3A (see Appendix E) should be avoided in the study. If a participant requires a strong CYP3A inhibitor or inducer while on treatment with acalabrutinib, acalabrutinib treatment must be discontinued. Refer to Section 6.5.4 for additional information on drugs with potential drug-drug interactions.

**Other BTK inhibitors:** BTK inhibitors other than acalabrutinib are prohibited.

**Certain anticoagulants:** Warfarin or equivalent vitamin K antagonists (eg, phenprocoumon) are prohibited in the study. Participants who require prophylaxis or therapeutic anticoagulation for thrombosis (deep vein thrombosis or pulmonary embolism) will be allowed to receive therapeutic anticoagulation with a non-vitamin K inhibitor class of anticoagulants (eg, heparin or low-molecular-weight heparin).

Refer to Section 5.2 for additional restrictions on concomitant therapy.

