## **B 3 A Guide to Interpreting the Causality Question**

When assessing causality consider the following factors when deciding if there is a 'reasonable possibility' that an AE may have been caused by the drug.

- Time course. Exposure to suspect drug. Has the participant actually received the suspect drug? Did the AE occur in a reasonable temporal relationship to the administration of the suspect drug?
- Consistency with known drug profile. Was the AE consistent with the previous knowledge of the suspect drug (pharmacology and toxicology) or drugs of the same pharmacological class? Or could the AE be anticipated from its pharmacological properties?
- De-challenge experience. Did the AE resolve or improve on stopping or reducing the dose of the suspect drug?
- No alternative cause. The AE cannot be reasonably explained by another aetiology such as the underlying disease, other drugs, other host or environmental factors.
- Re-challenge experience. Did the AE reoccur if the suspected drug was reintroduced after having been stopped? AstraZeneca would not normally recommend or support a re-challenge.
- Laboratory tests. A specific laboratory investigation (if performed) has confirmed the relationship.

In difficult cases, other factors could be considered such as:

- Is this a recognised feature of overdose of the drug?
- Is there a known mechanism?

Causality of ‘related’ is made if following a review of the relevant data, there is evidence for a ‘reasonable possibility’ of a causal relationship for the individual case. The expression ‘reasonable possibility’ of a causal relationship is meant to convey, in general, that there are facts (evidence) or arguments to suggest a causal relationship.

The causality assessment is performed based on the available data including enough information to make an informed judgment. With no available facts or arguments to suggest a causal relationship, the event(s) will be assessed as ‘not related’.

Causal relationship in cases where the disease under study has deteriorated due to lack of effect should be classified as no reasonable possibility.

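### The Safety Review Committee must meet for a Grade 4 hemorrhage only if the investigator blames acalabrutinib; the attribution condition should go

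*Protocol*

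**What the plan says.** Section 9.6 of the protocol provides for scheduled reviews, at an interval it does not state, and for a further meeting if either of two events occurs. One is a death due to acalabrutinib, in the investigator's judgement. The other is "Any Grade 4 hemorrhage due to acalabrutinib (per Investigator"). The members are the sponsor's study physician, the principal investigator or a delegate from active sites, "and Global Safety Physician or delegate". Further process is left to a charter, which is not shown. The synopsis states the committee's purpose: to "enable early identification of safety signals in the study, and minimize the risk to participants during the study".

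The surrounding facts, all from the protocol:

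- Design (synopsis, Disclosure Statement): "This is a single-arm, treatment study that is not blinded".
- Known risk (2.3.1.1): "Bleeding events, some fatal, including central nervous system, respiratory, and gastrointestinal hemorrhage, have been reported in participants treated with acalabrutinib".
- Background treatment (6.5.3): participants who need anticoagulation for thrombosis "will be allowed to receive therapeutic anticoagulation with a non-vitamin K inhibitor class of anticoagulants".
- Attribution (8.3.3 and Appendix B 3): a yes/no judgement on whether causation by the drug is a reasonable possibility. One factor asks "Was the AE consistent with the previous knowledge of the suspect drug". Another is the absence of an alternative cause: "The AE cannot be reasonably explained by another aetiology such as the underlying disease, other drugs".

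**The concern.** Grade 4 hemorrhage is the only non-death event that the protocol chose as a reason to convene the committee. Whether the meeting must happen then rests on one investigator's reading of one case. That reading is hard to make here. Participants have respiratory failure from COVID-19, a disease that section 2.2.1 links to coagulation abnormalities and thrombocytopenia; some will be anticoagulated; and no control arm shows how often such bleeds occur without the drug. Section 2.3.1 itself says that the safety profile in COVID-19 is not yet established.

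A drug effect that adds to anticoagulant bleeding could look, case by case, like anticoagulant bleeding. Several such cases side by side are what a cross-site committee is placed to notice. At stake is how soon sponsor physicians and site investigators must consider such an event together while other participants are still being dosed.

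**Working it through.** **Trigger logic.** The protocol gives no figure to reproduce on this point. Reading the two triggers in 9.6 against each kind of event gives:

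| Event | Rated related to acalabrutinib | Rated not related |
|---|---|---|
| Grade 4 bleed, not fatal | Meeting required (hemorrhage trigger) | No meeting required; next scheduled review |
| Fatal bleed | Meeting required (death trigger) | No meeting required; neither trigger met |

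Nothing elsewhere in the protocol fills the right-hand column. The synopsis mentions scheduled reviews only and points to 9.6 and the charter. Hemorrhage is not an adverse event of special interest; 8.3.12 lists only ventricular arrhythmias.

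**What does not depend on attribution to acalabrutinib.**

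- Table 7 (6.6) discontinues acalabrutinib for Grade 3 or 4 hemorrhage.
- Section 8.3.9 sends every serious adverse event to the sponsor within 24 hours. One qualification: 8.3.7 takes events unequivocally due to COVID-19 pneumonia out of reporting, while 8.3.8 keeps such events reportable if they meet the seriousness criteria.
- Section 8 requires immediate safety concerns to be discussed with the sponsor at once.
- Section 4.4 lets the sponsor stop the study for undue risk.

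These protect the participant who bled and inform the sponsor. None of them obliges the committee to meet.

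**Length of the delay.** It cannot be computed. The protocol gives no Grade 4 bleeding rate, no bleeding rate in COVID-19, no attribution rate and no review interval.

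**Cost of removing the condition.** This can be bounded. Inputs: about 20 participants (9.2), and an assumed probability p that a participant has a Grade 4 or 5 bleed, counting at most one meeting per participant.

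Expected extra meetings ≤ 20 × p

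- p = 1%: 20 × 0.01 = 0.20
- p = 2.7%: 20 × 0.027 = 0.54
- p = 5%: 20 × 0.05 = 1.00
- p = 10%: 20 × 0.10 = 2.00

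The bound stays below one meeting while p < 1/20 = 5%. It is an upper bound because bleeds rated related already trigger a meeting.

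The 2.7% is 28/1040 from Table 2 and is only a rough reference. It counts Grade 3 or higher hemorrhage under long-term oncology dosing, where the median time to first major hemorrhage was 9.8 months; dosing here lasts 14 days. Shorter dosing and the higher grade point to a lower rate, critical illness and anticoagulation to a higher one.

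**The case against.** The strongest reply is that nothing is misstated and little is lost. Scheduled reviews carry no attribution filter, so an unattributed bleed waits for the next one at most. The aim of early signal detection appears in the synopsis in the sentence about scheduled reviews, so 9.6 does not contradict it. Section 9.6 sets a minimum and bars no other meeting, and the charter may set a short interval or add triggers. All of this stands, and it limits the consequence to a possible delay.

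The attribution threshold is also low. Only a reasonable possibility is needed, an alternative cause is one factor among several, and bleeding fits the known drug profile. A mixed-cause bleed may well be rated related. That stands too: the gap covers only bleeds rated not related. But the threshold is applied by one person without a comparator, and a low threshold does not remove the dependence on that person.

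Eligibility limits bleeding risk: recent stroke or intracranial hemorrhage, platelets below 50,000/µL, vitamin K antagonists, and antiplatelet treatment combined with therapeutic anticoagulation are excluded (5.2). These limits lower the event rate. They do not make a bleed under permitted heparin easier to attribute.

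The comparisons with 8.3.12 and Table 7 are imperfect, since one governs expedited reporting and the other dosing. They show that the protocol uses attribution-free rules where it wants prompt action, not that 9.6 is inconsistent.

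Finally, the change leaves the similarly worded death trigger alone. There is a reason. Section 2.2.1 cites mortality of nearly 50% in mechanically ventilated patients; if all 20 participants carried that risk, an unconditional death trigger would fire about 20 × 0.5 = 10 times. Bleeds of Grade 4 or 5 are not expected at anything like that frequency under the assumed rates.

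**Conclusion.** The concern holds as a reading of the protocol. Section 9.6 creates no obligation to convene the committee for a Grade 4 bleed, or a fatal one, that the investigator does not ascribe to acalabrutinib. The consequence is modest: a possible delay in joint study-level review of unknown length, with no loss of data and no unprotected participant. It is worth correcting because bleeding is a recognised risk of the drug, attribution is difficult in this setting, and the correction is nearly free. Confidence is medium, since the charter is not shown and could already close the gap in practice. The cost range of 0.2 to 1.0 extra meetings rests on assumed rates of 1% to 5%; a higher rate would raise it in proportion.

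**What to change.** In 9.6, replace the hemorrhage trigger with: *Any Grade 4 or 5 hemorrhage, irrespective of investigator attribution*. Including Grade 5 brings in fatal bleeds rated unrelated. Leave the death trigger, the dosing rules and the scheduled reviews as they are.

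The change is one line in 9.6, and one in the charter if it repeats the trigger. It uses the existing committee and data already collected, and can go into the next amendment. The only running cost is an occasional additional ad hoc meeting, within the bound worked out above.

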## **10 SUPPORTING DOCUMENTATION AND OPERATIONAL CONSIDERATIONS**

## **Appendix A Regulatory, Ethical, and Study Oversight Considerations**

### **A 1 Regulatory and Ethical Considerations**

- This study will be conducted in accordance with the protocol and with the following:
  - Consensus ethical principles derived from international guidelines including the Declaration of Helsinki and Council for International Organizations of Medical Sciences International Ethical Guidelines
  - Applicable ICH GCP Guidelines
  - Applicable laws and regulations
- The protocol, protocol amendments, ICF, IB, and other relevant documents (eg, advertisements) must be submitted to an IRB/IEC by the Investigator and reviewed and approved by the IRB/IEC before the study is initiated.
- Any amendments to the protocol will require IRB/IEC and applicable Regulatory Authority approval before implementation of changes made to the study design, except for changes necessary to eliminate an immediate hazard to study participants.
- AstraZeneca will be responsible for obtaining the required authorizations to conduct the study from the concerned Regulatory Authority. This responsibility may be delegated to a CRO but the accountability remains with the Sponsor.

### **Regulatory Reporting Requirements for SAEs**

- Prompt notification by the Investigator to the Sponsor of a SAE is essential so that legal obligations and ethical responsibilities towards the safety of participants and the safety of a study intervention under clinical investigation are met.
- The Sponsor has a legal responsibility to notify both the local regulatory authority and other regulatory agencies about the safety of a study intervention under clinical investigation. The Sponsor will comply with country-specific regulatory requirements relating to safety reporting to the regulatory authority, IRB/IEC, and Investigators.
- For all studies except those utilizing medical devices, Investigator safety reports must be prepared for SUSAR according to local regulatory requirements and Sponsor policy and forwarded to Investigators as necessary.
- An Investigator who receives an Investigator safety report describing a SAE or other specific safety information (eg, summary or listing of SAEs) from the Sponsor will review and then file it along with the IB and will notify the IRB/IEC, if appropriate according to local requirements.

### **A 2 Financial Disclosure**

Investigators and sub-investigators will provide the Sponsor with sufficient, accurate financial

information as requested to allow the Sponsor to submit complete and accurate financial certification or disclosure statements to the appropriate regulatory authorities. Investigators are responsible for providing information on financial interests during the course of the study and for 1 year after completion of the study.

### **A 3 Informed Consent Process**

The Investigator or his/her representative will explain the nature of the study to the participant or his/her legally authorized representative and answer all questions regarding the study.

Participants or their legally authorized representative must be informed that their participation is voluntary, and they are free to refuse to participate and may withdraw their consent at any time and for any reason during the study. Participants or their legally authorized representative will be required to sign a statement of informed consent that meets the requirements of 21 CFR 50, local regulations, ICH guidelines, HIPAA requirements, where applicable, and the IRB/IEC or study center.

The medical record must include a statement that written informed consent was obtained before the participant was enrolled in the study and the date the written consent was obtained. The authorized person obtaining the informed consent must also sign the ICF.

Participants must be re-consented to the most current version of the ICF(s) during their participation in the study.

A copy of the ICF(s) must be provided to the participant or the participant's legally authorized representative.

Participants will be told that they are free to refuse to participate and may withdraw their consent at any time and for any reason during the sample storage period. If a participant withdraws consent to the use of donated biological samples, the samples will be disposed of/destroyed, and the action documented. If samples already have been analyzed at the time of the request, the Sponsor will not be obliged to destroy the results of this research.

### **A 4 Data Protection**

Each participant will be assigned a unique identifier by the Sponsor. Any participant records or datasets that are transferred to the Sponsor will contain the identifier only; participant names or any information which would make the participant identifiable will not be transferred.

The participant must be informed that his/her personal study-related data will be used by the Sponsor in accordance with local data protection law. The level of disclosure and use of their data must also be explained to the participant in the informed consent

The participant must be informed that his/her medical records may be examined by Clinical Quality Assurance auditors or other authorised personnel appointed by the Sponsor, by appropriate IRB/IEC members, and by inspectors from regulatory authorities.

## **A 5 Dissemination of Clinical Study Data**

A description of this clinical study will be available on <http://astrazenecagrouptrials.pharmacm.com> and <http://www.clinicaltrials.gov> as will the summary of the study results when they are available. The clinical study and/or summary of study results may also be available on other websites according to the regulations of the countries in which the study is conducted.

## **A 6 Data Quality Assurance**

All participant data relating to the study will be recorded on eCRF unless transmitted to the Sponsor or designee electronically (eg, laboratory data). The Investigator is responsible for verifying that data entries are accurate and correct or electronically signing the eCRF.

The Investigator must maintain accurate documentation (source data) that supports the information entered in the eCRF.

The Investigator must permit study-related monitoring, audits, IRB/IEC review, and regulatory agency inspections and provide direct access to source data documents.

The Sponsor or designee is responsible for the data management of this study including quality checking of the data.

The Sponsor assumes accountability for actions delegated to other individuals (eg, Contract Research Organizations).

Study monitors will perform ongoing source data verification to confirm that data entered into the eCRF by authorized site personnel are accurate, complete, and verifiable from source documents; that the safety and rights of participants are being protected; and that the study is being conducted in accordance with the currently approved protocol and any other study agreements, ICH GCP, and all applicable regulatory requirements.

Records and documents, including signed ICFs, pertaining to the conduct of this study must be retained by the Investigator for 15 years after study completion unless local regulations or institutional policies require a longer retention period. No records may be destroyed during the retention period without the written approval of the Sponsor. No records may be transferred to another location or party without written notification to the Sponsor.

## **A 7 Source Documents**

Source documents provide evidence for the existence of the participant and substantiate the integrity of the data collected. Source documents are filed at the Investigator's site.

Data entered in the eCRF that are transcribed from source documents must be consistent with the source documents or the discrepancies must be explained. The Investigator may need to request previous medical records or transfer records, depending on the study. Also, current medical records must be available.

Definition of what constitutes source data can be found in in the Clinical Study Agreement.

## **A 8 Study and Site Start and Closure**

The Sponsor designee reserves the right to close the study site or terminate the study at any time for any reason at the sole discretion of the Sponsor. Study sites will be closed upon study completion. A study site is considered closed when all required documents and study supplies have been collected and a study-site closure visit has been performed.

The Investigator may initiate study-site closure at any time, provided there is reasonable cause and sufficient notice is given in advance of the intended termination.

Reasons for the early closure of a study site by the Sponsor or Investigator may include but are not limited to:

- Failure of the Investigator to comply with the protocol, the requirements of the IRB/IEC or local health authorities, the Sponsor's procedures, or GCP guidelines
- Inadequate recruitment of participants by the Investigator
- Discontinuation of further study intervention development

If the study is prematurely terminated or suspended, the Sponsor shall promptly inform the Investigators, the IECs/IRBs, the regulatory authorities, and any contract research organization(s) used in the study of the reason for termination or suspension, as specified by the applicable regulatory requirements. The Investigator shall promptly inform the participant and should assure appropriate participant therapy and/or follow-up.

## **A 9 Publication Policy**

The results of this study may be published or presented at scientific meetings once the primary analysis is completed and the study is unblinded. No other publications prior to that time point is allowed.

The Sponsor will comply with the requirements for publication of study results. In accordance

with standard editorial and ethical practice, the Sponsor will generally support publication of multicenter studies only in their entirety and not as individual site data. In this case, a coordinating Investigator will be designated by mutual agreement.

Authorship will be determined by mutual agreement and in line with International Committee of Medical Journal Editors authorship requirements.

Subsequent to the primary publication, if an Investigator plans to publish any subset of data, or case report, the Investigator agrees to submit all manuscripts or abstracts to the Sponsor before submission. This allows the Sponsor to protect proprietary information and to provide comments.

